15.1 Partial Dates

In the case that only partial dates are available for adverse events, the dates will be imputed. If only the month and year are known, any duration calculated with the partially known date will assume that the date is the first day of the known month. If only the year is known, any duration calculated with the partially known date will assume that the date is July 1 of the known year. In the event that the imputed date is before the procedure date, the imputed date will be equal to the procedure date. If the imputed date is after the last follow-up date or event resolution date, the imputed date will be the latest possible date.

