11.1.1 Primary Endpoint: Analysis of Adverse Events

Adverse events will be presented in summary tables displaying the number of events, the number of enrolled subjects with ≥ 1 event, and the proportion of enrolled subjects with ≥ 1 event. The rates of adverse events will serve as the primary analysis.

Adverse event analysis may be repeated for only those events that occur after the initiation of treatment with rates calculated as a proportion of treated subjects..

Phase

The timing of adverse events relative to the initial LITT procedure will be tabulated by reporting the event counts, subject counts, and subject rates of events that occur within the following phases:

- **Baseline:** Prior to LITT procedure
- **Operative:** From the beginning of the LITT procedure through 30 days post-procedure
- **Year 1:** From 31 days post-procedure through 12 study months (12 month visit date or close of 12 month visit window if 12 month visit is missed)
- **Year 2:** After 12 study months through 24 study months (24 month visit date or close of 24 month visit window if 24 month visit is missed)

Additional analyses may be performed that divide the above phases into more detailed time intervals or that combine phases to present an overall summary of all adverse events through a specific time point (e.g. Operative Through Year 2).

Severity

The severity of adverse events will be tabulated by reporting the event counts, subject counts, and subject rates of events that are:

- **Mild:** Does not interfere in a significant manner with the subject's normal functioning level.
- **Moderate:** Produces some impairment of functioning but is not hazardous to health.
- **Severe:** Produces significant impairment of function or incapacitation and is a hazard to the subject's health.

Relationship

The relationship of adverse events to the device treatment or procedure will be tabulated by reporting the event counts, subject counts, and subject rates of events based on the following relationship categories:

- **Definite** – The adverse event follows a strong temporal sequence to the receipt (or attempted receipt) of the device treatment or procedure. This can include an adverse event that occurs after the study procedure.

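### SAP 15.1 imputes partial adverse-event onset dates without using the contact dates, so an onset can be dated after it was reported and filed in the wrong phase

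*SAP*

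**What the plan says.** SAP 15.1 covers adverse events with incomplete dates. With month and year known: "If only the month and year are known, any duration calculated with the partially known date will assume that the date is the first day" in that month. With the year alone: "If only the year is known, any duration calculated with the partially known date will assume that the date is July 1" in that year. Two limits follow. The lower one is the procedure: "In the event that the imputed date is before the procedure date, the imputed date will be equal to the procedure date". The upper one is: "If the imputed date is after the last follow-up date or event resolution date, the imputed date will be the latest possible date". The SAP does not define that latest date.

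SAP 11.1.1, under the primary endpoint, tabulates event counts, subject counts and subject rates by phase. Baseline is "Prior to LITT procedure", Operative is "From the beginning of the LITT procedure through 30 days post-procedure", and Year 1 is "From 31 days post-procedure through 12 study months", ending at the 12-month visit or the close of its window. Year 2 follows.

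Protocol 7.6 has adverse events asked about at discharge, Day 14, Month 1 and then at a visit or call every month to Month 24. Protocol 9.1 starts collection on the day of the procedure. SAP 12.3 defines a study month as 28 days.

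**The concern.** Each event is first recorded at a known contact, usually within about a month of the one before. Those two dates normally bracket the onset far more tightly than a calendar year, and often more tightly than a calendar month. SAP 15.1 uses neither.

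A year-only onset can therefore be placed later than the contact at which the event was reported, which cannot be right under any reading. A month-only onset can be placed before a contact at which the event was not mentioned, which is doubtful though not impossible.

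The phase table is where this matters, because the split between Operative and Year 1 is how a reader separates harm around the procedure from later harm. July 1 dating can move operative events out of the Operative row; first-of-month dating can move later events in. With 30 to 45 enrolled subjects (SAP section 9), one misfiled subject moves a phase rate by 1/45 to 1/30, or 2.2 to 3.3 percentage points.

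**Working it through.** **Inputs.** Imputation rule and limits: SAP 15.1. Phase cuts: SAP 11.1.1 (Operative is days 0-30). Month length: SAP 12.3, so Month 1 is day 28 and Month 2 is day 56. Assumptions not in the documents: surgery equally likely on each of 365 days, onset uniform over the stated days, report at the first contact after onset, and the undefined upper date read as the resolution date for resolved events.

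**The plan's own figure.** The SAP gives none for partial dates. Its sample-size figure reproduces: 1 - 0.95^30 = 0.785, stated as about 80%. Nothing below depends on it.

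**Year-only, unresolved, onset on days 0-28.** There are 365 x 29 = 10,585 combinations of surgery date and onset day.
- July 1 is day 31 for surgery on May 31 and day 30 for surgery on June 1. Surgery from January 1 to May 31 (151 dates) therefore gives Year 1: 151 x 29 = 4,379.
- December surgery with onset in January is dated to July 1 of the next year, also Year 1. Onset day t has t such surgery dates: 1 + 2 + ... + 28 = 406.
- In all other cases July 1 falls within 30 days of surgery, or before it and is raised to the procedure date: Operative.
- Filed as Year 1: (4,379 + 406) / 10,585 = **45.2%**. All are truly Operative.

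**Year-only, resolved after L days.** The resolution cap is day t + L, so Year 1 also requires t + L > 30.
- L = 7, t = 24 to 28: (151 x 5 + 130) / 10,585 = 885 / 10,585 = **8.4%**.
- L = 14, t = 17 to 28: (151 x 12 + 270) / 10,585 = 2,082 / 10,585 = **19.7%**.
- L = 30, t = 1 to 28: (151 x 28 + 406) / 10,585 = 4,634 / 10,585 = 43.8%.

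Example: surgery on 10 January 2018, onset on day 5, reported at Day 14, ongoing. The rule gives 1 July, day 172, Year 1.

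With the reporting contact as a cap, an onset by day 28 is reported by day 28, so the imputed day cannot exceed 28: **0%** misfiled.

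**Month-only.** The first of the onset month, or the procedure date if later, never falls after the true onset, so it never falls after the report. Errors run only towards the earlier phase.
- Onset on days 29-56. Days 29 and 30 are always filed as Operative. For t from 31 to 56, the chance that no month begins between day 31 and day t is 1 - 12(t - 30)/365. The average is (28 - 12 x 351/365) / 28 = **58.8%** filed as Operative. The true share is 2/28 = 7.1%.
- Example: surgery on 15 March 2018, onset on 24 April (day 40, Year 1), dated 1 April (day 17, Operative).
- Enumerating all surgery dates, 47% of onsets on days 31-61 are filed as Operative and 47% of those on days 337-367 as Year 1. Over onsets spread evenly to day 672, 4.4% change phase.

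**Which date within the contact interval.** Take the same month-only events on days 29-56, last contact without the event at day 28.
- Earliest compatible day: whenever the first of the month is on or before day 30, the earliest allowed day is 29 or 30, still Operative. The share stays at 58.8%.
- Midpoint (rounded down): 1.2% filed as Operative.
- At the 12-month cut the boundary is itself a contact, so the lower bound alone removes the shift.

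**The case against.** The strongest reply is that this will rarely matter. With contacts about monthly, an onset known only to the year should be uncommon, and every percentage above is conditional on a partial date whose frequency the documents do not give. That stands, and it keeps the point minor.

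Four stronger readings are tempting and are not supported.
- A reader might infer that surgery on or before May 31 always sends a year-only event to Year 1. The resolution cap prevents that for events resolved by day 30, hence 8% to 20% rather than 45% for short events.
- A reader might infer that the headline safety rate is wrong. That rate is the proportion of enrolled subjects with at least one event, which does not depend on onset date. Relatedness, adjudicated where available (SAP 15.3), also helps to separate procedural from later harm.
- A reader might call the month-only dates impossible. They never fall after the report. A date before the previous contact is ruled out only if the event would have been mentioned there, and late recall is ordinary.
- A reader might apply the rule to resolution dates and find resolutions before onset. The rule uses the resolution date as a cap, so it reads as an onset rule, and SAP 11.1.1 plans no table of event duration.

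What remains is that SAP 15.1 lets an onset be dated after its own report and move across a phase cut, although the dates that would prevent this are collected.

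**Conclusion.** The point holds as a minor defect confined to the phase breakdown in SAP 11.1.1. For year-only onsets on days 0-28, about 45% of unresolved events and about 8% to 20% of events lasting 7 to 14 days would be filed as Year 1 when they are Operative. For month-only onsets, events near the day-30 and 12-month cuts drift to the earlier phase. These sizes assume surgery uniform over the year, uniform onset within the stated days, 28-day contacts and prompt reporting. They apply only to events with partial dates, whose number is unknown.

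**What to change.** Rewrite the paragraph in SAP 15.1 so that an imputed onset must:
- fit the known month or year;
- be no earlier than the procedure;
- be later than the last contact without the event, unless the site records late reporting;
- be no later than the earliest of the reporting contact, the resolution and the end of follow-up.

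Use the midpoint of that interval. The earliest day would leave the day-30 shift untouched. Define the latest possible date as that upper bound, and state that the rule applies to onset dates.

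The cost is one paragraph and minor programming, using contact dates already collected on the case report forms. The midpoint slightly under-assigns events to Operative at the day-30 cut (about 1% against a true 7% for month-only onsets on days 29-56). With Month 1 at day 28, only onsets on days 29 and 30 can be lost this way: at most 2 of the 31 Operative days, or 6.5% of partial-date Operative onsets if these are uniform.

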15.2 Visit Windows

All data attributed to a time point per the CRF will be included in the analysis of that time point, regardless of whether the actual visit date was out of window.

15.3 CEC Adjudication

In all tabulations of adverse events, the categorizations of adverse events determined by the CEC (e.g. relatedness of adverse events to the device treatment or procedure) will be reported, if available, and categorizations provided by investigators will be reported otherwise. Adverse event listings will report both CEC and investigator categorizations.

16 Interim Analyses

Analyses will be reported on data from baseline through a major study time point once all subjects have completed that major study time point (e.g., 6 months, 12 months and 24 months). There is minimal opportunity for bias since all procedures will have been completed before any analysis is reported and all data will have been collected for a time point before analysis of that time point is reported.

The study's DSMB may request descriptive analyses of accumulating data at its discretion.

17 Missing Data Analyses

Every effort will be made to reduce the incidence of missing data. The study will be conducted with proper screening of study subjects, complete training of participating investigators, study coordinators and monitors. All subject data that are available on subjects who drop out during the study will be included.

The number and proportion of subjects eligible for and compliant with each follow-up examination will be presented. Subjects who withdraw from the study will be tabulated with reasons for withdrawal. Sensitivity analyses, such as multiple imputation or worst case imputation, may be performed to assess the robustness of study conclusions to the potential impact of missing data.

In worst case imputation, for binary endpoints the worse of the two possible outcomes will be imputed. The timing of the imputed event will be the last known event-free date for subjects that exit the study prematurely. For continuous endpoints assessed at a single time period (e.g. quality of life), the worst observed value among subjects with observed data at that time period will be imputed for subjects with missing data. For rates corresponding to a specific follow-up time interval, any partial observed data for a subject will be used. Data for the missing portion of the subject's follow-up time interval will be imputed using the worst observed value among all subjects with observed data during the corresponding missing portion of the follow-up time interval, in order to calculate an imputed rate for the overall follow-up time interval.

18 Sensitivity Analyses

Sensitivity analyses may be performed to describe the potential impact of various factors on the observed study results.

18.1 Medication and Concomitant Epilepsy Treatment

Changes to medications have the potential to impact the study endpoints and may be confounded with the impact of the investigational treatment. The analyses described below can provide insight into the potential impact of medication changes.

1. Subjects that had significant changes to the AED regimen (e.g., dosage change, discontinued AED, or new AED) between the Baseline Week -12 visit and the Month 24 visit will be excluded from analyses of visits after the AED changes occur (data censored after medication change).

Additionally, compare observed (uncensored) results at different follow-up time points between the 4 groups of subjects below. The AED regimen change group is determined by changes that occur prior to the follow-up time point being evaluated.

- (a) No change in AED regimen (same medications and dosage compared to baseline)
- (b) Increase in AED regimen (increased number of medications or dosage compared to baseline)
- (c) Decrease in AED regimen (decreased number of medications or dosage compared to baseline)

(d) Other AED regimen change (increased dosage of a medication or addition of a new medication and decreased dosage or discontinuation of a different medication compared to baseline)

2. Subjects that had clinically significant changes to other concomitant epilepsy treatment (e.g., other surgical procedures, vagal nerve stimulation) between the Baseline Week -12 visit and the Month 24 visit will be excluded from analyses of visits after the changes to concomitant epilepsy treatment occur (data censored after concomitant epilepsy treatment change).

19 Poolability of Data

This study is designed and conducted as a multicenter clinical trial. All participating sites will be selected using the same criteria and trained prior to enrolling subjects. All subjects will be treated and evaluated following the same protocol to ensure generalizability of the study results. Poolability of the data across centers in a multicenter study is assumed without burden of proof.

Nevertheless, poolability of data across sites will be examined for apparent violation of the poolability assumption. The results of a poolability analysis will be used to assess the robustness of the study results, but not to change the study conclusion. For the primary outcomes, the rate of related adverse events and rate of changes exceeding the reliable change index for each core neuropsychological test will be performed separately for each participating institution. Additionally, a chi-square statistic will be used to describe the degree of variation in these proportions across sites.

For the seizure outcomes secondary objective, a Poisson regression will be performed with the post-procedure event rate over 24 months as the response variable and baseline event rate and site as explanatory factors, to assess variation in post-procedure seizure rates across sites.

For the quality of life secondary objective, an analysis of variance (ANOVA) will be used to assess homogeneity of the mean change in QOLIE-31 scores across sites at 24 months.

Sites with fewer than 5 subjects will be combined into a “small numbers” site for these analyses since the smaller the number of enrollments at a site, the less likely it is that the observed results reflect the expected results if the site had a greater number of enrollments. Results may also be presented separately for each site to describe the study endpoints across sites.

20 Deviations from the Statistical Analysis Plan

Any deviation from these planned statistical methods will be documented and discussed in the clinical study report along with statistical rationale for deviation.

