7 STUDY METHODOLOGY

7.1 Trial Summary

Subjects who meet the study eligibility criteria and sign the informed consent form (ICF) will undergo a Baseline visit for initial evaluations, testing and collection of demographics and medical history.

The LITT surgical procedure will be performed within 30 days of the Baseline visit. After the procedure, subjects will be seen for a brief visit prior to discharge from the hospital and again at the Day 14 visit. Subject visits will continue with office visits at Months 1, 3, 6, 9 and 12. After the Month 12 visit, subjects will have semi-annual office visits, at Months 18 and 24. Starting at Month 2, subjects will have

⁴ Exclusion criteria may need to be evaluated after obtaining informed consent, if it not part of the Site's standard of care for epilepsy management and/or surgery evaluation.

interim monthly phone calls (the months that the subject is not seen for an office visit). Investigators will keep AEDs stable through the Month 12 visit.

The study design is outlined in Figure 3.

[figure not shown]

Figure 3: Study Design Schema

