APPENDIX A MEDICATIONS

All prescription medications (epilepsy and non-epilepsy) that the subject is taking during the course of the trial will be recorded on a CRF. Epilepsy medications will be recorded on the *Epilepsy Medication Log* CRF. Non-epilepsy medications will be recorded on the *Concomitant Medication Log* CRF. Documentation of perioperative medications and anesthetic agents is only required for steroids and for medications used to treat an intraoperative adverse event.

Additionally, all epilepsy medications that the subject took in the year preceding the Baseline visit will be recorded on the *Epilepsy Medication Log* CRF. Collection of retrospective rescue medication use is not required.

AEDs

No changes in AED total daily doses are allowed between the Baseline visit and the Month 12 visit with the following exceptions: (1) temporary periprocedural discontinuation or modification for clotting considerations (e.g., valproic acid/valproate), (2) if the clinical condition of the subject warrants modification/discontinuation.

If there is a change, record the changes on the *Epilepsy Medication CRF* and document on a *Protocol Deviation CRF*.

Acute (Rescue) AEDs

In many epilepsy centers, a standard of care for uncontrolled epilepsy is the use of intermittent “rescue” medications (e.g., acute benzodiazepines). These medications are used by the subject on an “as needed” basis to either abort a prolonged seizure or to prevent a cluster of seizures from occurring. If the protocol excluded subjects who used rescue medications the subject pool would decrease substantially. Therefore, the protocol will allow the use of rescue medications during the study. Rescue medications will be recorded on the *Epilepsy Medication CRF*.

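### The AED-change sensitivity analysis in SAP 18.1 removes later visits on a trigger that can depend on outcome and, read literally, drops subjects for a permitted temporary hold around surgery

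*SAP*

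**What the plan says.** SAP 18.1 item 1 identifies "Subjects that had significant changes to the AED regimen (e.g., dosage change, discontinued AED, or new AED") occurring "between the Baseline Week -12 visit and the Month 24 visit". These subjects "will be excluded from analyses of visits after the AED changes occur (data censored after medication change"). The text gives no definition of significant, no size or duration limit, no exemption for temporary changes, and no way back into the analysis once the earlier regimen is restored.

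The same item then asks the analyst to "compare observed (uncensored) results at different follow-up time points between the 4 groups of subjects below". The groups are (a) no change from baseline, (b) increase, (c) decrease and (d) a mixture. Nobody is dropped from this comparison.

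Protocol Appendix A bars changes in total daily AED dose from Baseline to Month 12, with two exceptions: "temporary periprocedural discontinuation or modification for clotting considerations", and "if the clinical condition of the subject warrants modification/discontinuation". Any change goes on the epilepsy medication form and on a protocol deviation form. Protocol 7.1 says "Investigators will keep AEDs stable through the Month 12 visit"; no stability requirement is stated for Months 12 to 24. SAP 12.7 names 24 months as a time point of primary interest.

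SAP 18 makes these analyses optional: "Sensitivity analyses may be performed to describe the potential impact of various factors on the observed study results".

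**The concern.** The analysis is meant to show how far AED changes could explain the results. It works by removing a subject's later visits once the regimen changes. That is harmless only if the change is unrelated to how the subject is doing.

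Under the protocol it may well be related. Apart from the periprocedural exception, a dose change before Month 12 is allowed only when the subject's clinical condition calls for it, and persisting seizures are one such reason. After Month 12 no restriction is stated, so regimens may also be reduced in subjects who are doing well. The first kind of change removes failures from later visits; the second removes successes. The censored result can then differ from the main result, or agree with it, for reasons unrelated to any drug effect.

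A second problem is mechanical. The counting window spans surgery and a discontinued AED is a listed trigger, so a short permitted hold precedes every follow-up visit.

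This is an uncontrolled study, and 18.1 is the SAP section that addresses AED confounding. A misread result there would leave the question without a sound answer.

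**Working it through.** **The plan's own figure.** SAP 9 says an adverse event with 5% per-subject probability has about an 80% chance of appearing at least once in 30 subjects. 1 − 0.95^30 = 0.785, which agrees. The present point does not rest on it.

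**Inputs.** N = 30 comes from SAP 9. The documents give no responder share and no rate of AED increase, taper or hold. The following are therefore assumptions:
- p, the true responder share: 60%, varied from 40% to 60%.
- u, the share of non-responders with AEDs raised before the visit: 0 to 60%.
- t, the share of responders tapered before the visit: 0 to 60%.
- AED changes have no effect on outcome.

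**Step 1: visit-based proportion after exclusion.** Estimate = p(1 − t) / [p(1 − t) + (1 − p)(1 − u)]. With p = 60% there are 18 responders and 12 non-responders.
- u = 25%, t = 0: 18 / (18 + 9) = 18/27 = 67%.
- u = 50%, t = 0: 18 / (18 + 6) = 18/24 = 75%.
- u = 25%, t = 50%: 9 / (9 + 9) = 9/18 = 50%.
- u = 50%, t = 50%: 9 / (9 + 6) = 9/15 = 60%, unbiased but with half the subjects gone.

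Over p = 40% to 60% and the pairs of t and u tried, the estimate runs from 25% (p = 40%, t = 50%, u = 0: 0.20/0.80) to 75% (p = 60%, t = 0, u = 50%: 0.60/0.80). The bias can be up, down or nil.

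**Step 2: Kaplan-Meier freedom from seizures with altered awareness.** SAP 11.1.3 uses the first seizure after the excluded first 4 weeks. A subject whose counted seizure came before the AED increase stays an event, so later censoring does not remove that failure. Tapering was simulated in 200,000 subjects. Half never seize; in the rest the first seizure comes at 1 month plus an exponential time with mean 6 months. Half of the never-seizing subjects are tapered at a uniform time between Months 12 and 24. All of these inputs are assumptions. The 24-month estimate moves from 51.1% to 49.7%. When tapering is unrelated to risk among those seizure-free at Month 12, the figures are 51.0% and 51.1%. The remaining exposure is an increase made before the first counted seizure, for example after seizures in the first 4 weeks.

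**Step 3: periprocedural hold.** If a hold counts as significant, every post-procedure visit follows it. For an assumed 5% to 30% of subjects held, 30 × 0.95 = 28.5 down to 30 × 0.70 = 21 remain with any follow-up visit in the censored analysis. Group (a) of the same item is defined by regimen relative to baseline. A subject back on the baseline regimen therefore fits no change in one half of item 1 and is excluded in the other.

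**Step 4: window start.** The window opens at a Week -12 baseline visit. That visit is in the SAP schedule, and SAP 3 cites protocol Rev A. Rev B, Table 1, has a single Baseline visit, so the window has no defined start under the current protocol.

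**The case against.** The other side has several fair points, and most of them stand.

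- A reader might infer that any AED change triggers exclusion. The SAP says significant changes. The gap is that the word is undefined while its examples are broad. Data before the change are kept.
- A reader might infer that the rule favours the device, raising the success rate at Month 12 in particular. The documents do not establish a direction. The clinical-condition exception could cover intolerance as well as seizures, no passage says who would be tapered, and no change rates are given. Step 1 shows that the biases can cancel.
- Item 1 does not ignore direction altogether. Its uncensored comparison separates increases from decreases and keeps every subject, which partly offsets the problem. It is not a full answer: the groups are formed by post-treatment changes, and group (a) at a given visit is nearly the same set as the censored analysis.
- The hold is a literal reading. The exception is narrow, and inclusion criterion 4 already treats temporary procedural changes as compatible with stable AEDs. The censoring rule nevertheless states no exemption.
- Counting AED increases as failures answers a different question. If 25% of responders had a seizure-driven increase (an assumption), 18 × 0.75 = 13.5, and 13.5/30 = 45% with no AED effect. Nor does that rule fit seizure rates, QOLIE-31 or neuropsychological scores. This argues against replacing item 1 outright.

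**Conclusion.** The point holds for visit-based results in the censored part of item 1. Exclusion there can depend on outcome, so the result can be biased in either direction when AEDs do nothing. Under the assumed rates a true 60% responder share appears as 50% to 75%; the documents supply neither the 60% nor the rates, so this shows possible size and is not a forecast. A permitted temporary hold can, read literally, remove a subject from all follow-up visits, at odds with group (a) of the same item.

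The reach is limited. Kaplan-Meier time to first seizure moved by 51.1 − 49.7 = 1.4 points in the simulated case. The analysis is an optional supplement in a descriptive study without hypothesis tests. A reader might infer that the study's main seizure, quality-of-life or safety results are distorted; they are not, because the main analyses are not censored for AED change. The section is worth correcting before analysis because the correction is cheap.

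**What to change.** Amend SAP 18.1 as follows.

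1. State that temporary changes permitted by Protocol Appendix A that return to the baseline regimen do not count as an AED change. Define significant for everything else. This brings the censoring rule into line with group (a).
2. For binary seizure outcomes (responder, seizure-free), add a sensitivity analysis on the full Treated Set. Count a subject as a non-responder or not seizure-free from the date of a sustained AED increase or addition made for seizures, and keep observed data after a decrease. In the first three scenarios of Step 1, where increases occur only in non-responders, this returns 18/30 = 60% each time.
3. Keep the simple censored result only as a secondary display labelled as subject to informative censoring, including for seizure rates, QOLIE-31 and other continuous outcomes.
4. Use the reason for each change (seizures, side effect, taper after seizure freedom, periprocedural). Add it to the Epilepsy Medication Log if it is not already captured; the case report forms were not available for this review.
5. Replace the Week -12 window start with one that exists in protocol Rev B.

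The cost is SAP wording, one extra analysis and possibly one form field. The added result answers a composite question and will be somewhat less favourable to the device wherever responders had seizure-driven increases. No change to AED management is proposed.
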